7.1.3 Other study parameters

Questionnaires:

- Age
- Sex
- Ethnicity
- Socio-economic status
- Medical history and medication (history)
- Parental history
- Life-style (smoking, alcohol, drugs, stress)
- Oral hygiene

Physical examination:

- Blood Pressure (BP)
- Heart Rate (HR)
- Body Mass Index (BMI)
- Waist to Hip Ratio (WHR)
- Electrocardiogram (ECG)

Biochemical parameters:

- High sensitive C-reactive Protein (hsCRP)
- Total cholesterol
- High Density Lipoprotein (HDL) cholesterol
- Low Density Lipoprotein (LDL) cholesterol
- Triglycerides
- Estimated Glomerular Filtration Rate (eGFR)
- Glycated Hemoglobine (HbA1c)

Extra parameters for coupled studies:

One blood sample for DNA analysis of risk genes for both periodontitis and coronary heart disease.

Oral rinse sample for microbiological analysis of the oral microbiome peformed by pyrosequencing of 16Smicrobial DNA.

7.2 Randomisation, blinding and treatment allocation

Not applicable for this study.

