3. STUDY DESIGN

This is a cross-sectional (pilot) study, coordinated by the department of Oral and Maxillofacial Surgery of the Academic Medical Center (AMC), and the Department of Periodontology, ACTA, Amsterdam. Patients from the Practice for Periodontology Zwolle will be recruited. The department of Cardiology from the Isala Clinics will obtain the physical examinations, blood test, arterial stiffness test and the Coronary Calcium Score (CCS).

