4. STUDY POPULATION

4.1 Population (base)

Patients who visited the Practice for Periodontology Zwolle for either recently diagnosed periodontitis or dental implants.

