Endothelial dysfunction has been recognized as the critical junction between risk factors and clinical disease. It is the earliest detectable stage of cardiovascular disease. EndoPAT is a medical device for noninvasive endothelial function assessment. EndoPAT is based on noninvasive Peripheral Arterial Tone (PAT) signal technology. It measures endotheliummediated changes in vascular tone using unique bio-sensors placed on the fingertips. These changes in arterial tone are elicited by creating a down-stream hyperemic response induced by a standard 5-minute occlusion of the feeding artery (using a standard blood pressure cuff). When the cuff is released, the surge of blood flow causes an endothelium-dependent Flow Mediated Dilatation (FMD). The dilatation, manifested as Reactive Hyperemia, is captured by EndoPAT as an increase in the PAT Signal amplitude. A post-occlusion to preocclusion ratio is automatically calculated by the EndoPAT software, thus providing the EndoScore. Measurements from the opposite arm are used to control for concurrent nonendothelial dependent changes in vascular tone. EndoPAT tests can be carried out in both the office and hospital settings, with patients positioned either sitting or supine. The test takes 15 minutes to complete, is very easy to perform, and is both operator and interpreter independent.

Version number: 2 ,27 March 2013 14 of 23

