9. STATISTICAL ANALYSIS

Primary outcome is the correlation between the PISA score and the coronary calcium score. Therefore 2 groups of 25 patients will be analysed. One group diagnosed with periodontal disease and one group with a healthy periodontium. For description of the data the mean values, standard deviations, minimum and maximum are calculated. For continuous data, differences between the groups will be analysed using the independent T-test. If the data violates the assumption of a normal distribution, differences between the groups will be analysed using the Mann-Whitney test. Binary data will be assessed using the Pearson chi-square test. Correlation between the overall PISA score and the coronary calcium score will be calculated with the Spearman correlation test. Outcome variables that show significant between-groups differences at baseline will be used as covariate in a multivariate regression analysis. Data will be entered in a database (SPSS) and analyzed using SPSS statistical package 18.0 (SPSS Inc. Chicago, II

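### Section 7.2 sets blinding aside as not applicable, so nothing in the protocol keeps the reader of the coronary calcium score unaware of periodontal status

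*Protocol*

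**What the plan says.** Protocol section 7.2 is headed "7.2 Randomisation, blinding and treatment allocation", and its only content is "Not applicable for this study". No exception is made for outcome assessors.

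Five other places bear on the point:

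- **Section 9 (Statistical analysis):** "Primary outcome is the correlation between the PISA score and the coronary calcium score". It adds that "2 groups of 25 patients will be analysed", one with periodontal disease and one with a healthy periodontium, and it tests continuous data for differences between them.
- **Section 4.1 (Population):** the source is "Patients who visited the Practice for Periodontology Zwolle for either recently diagnosed periodontitis or dental implants".
- **Sections 3 and 7.3:** the periodontal examination is done at the periodontal practice. The CCS and EndoPAT are obtained by a hospital cardiology department, in a visit listed after the periodontal one.
- **Section 7.1.1:** PISA examiners are to be trained and calibrated. The EndoPAT "ratio is automatically calculated by the EndoPAT software, thus providing the EndoScore", and the test "is both operator and interpreter independent". The CCS paragraph explains why the score is a useful measure, but not who reads the scan or what that reader knows.
- **Section 11.1:** subjects carry a code of two letters and a running number, and the investigator holds the key.

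**The concern.** Three topics share one heading and receive one answer. Two of them do not arise here: nothing is randomised and no treatment is allocated. The third does. Masking the person who measures an outcome to the exposure of the subject is as possible in an observational comparison as in a trial, and it serves the same purpose.

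At stake is the primary result. The objective in section 2 covers both presence and extent of coronary calcification. Section 1 states the expected direction: the study may show periodontitis to be a risk indicator for atherosclerosis. If a reader knew the group and shared that expectation, doubtful scans could be scored differently in the two groups, and the correlation would move towards the hypothesis. Section 4.4 says that the pilot is meant to determine the size of a full study, so an inflated correlation here would lead to a later study that is too small.

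**Working it through.** The protocol gives no figure for reader agreement or assessment bias, so there is none to reproduce. The check is whether any section masks the CCS reader.

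**Step 1. Does the CCS reading enter the primary outcome?** Yes. Section 9 makes the PISA-CCS correlation primary. As a continuous variable, CCS could also be compared between the two groups (2 × 25 = 50, which agrees with the 50 participants in section 4.4).

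**Step 2. Does group information exist before the CCS is produced?** Yes. The reason for the visit, periodontitis or implants, is known at recruitment (4.1), and section 7.3 lists the periodontal examination before the cardiology visit.

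**Step 3. Does anything stop that information from reaching the reader?**

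| Provision | What it does | Masks the CCS reader? |
|---|---|---|
| 7.2 | Declares blinding not applicable | No |
| 3 and 7.3, separate sites | Makes masking easy | Not stated |
| 7.1.1, calibrated PISA examiners | Concerns the exposure measurement | No |
| 7.1.1, EndoPAT software | Protects the EndoScore | No |
| 11.1, subject code | Data handling; meaning of the two letters not given | Not stated |

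**Step 4. Does the same apply to EndoPAT?** Hardly. The value is computed by the device, the test is described as independent of operator and interpreter, and the EndoScore is not part of the primary correlation.

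**Step 5. Scale, under assumptions that are not in the protocol.**

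- One scan in a group of 25 is 1/25 = 4 percentage points of CCS > 0 prevalence. Two are 8 points and three are 12.
- With no true association, the standard error of a Spearman correlation in 50 subjects is 1/√(50 − 1) = 0.14.
- I simulated 50 subjects with no true association, PISA clearly separated between the groups, and CCS > 0 in 30% to 70%. Raising two or three zero scores in the periodontitis group to small positive values moved the correlation by about 0.02 to 0.07 on average. The chance of a falsely positive result in the upper tail rose from about 2.5% to about 4% to 8%.

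These results show what a one-sided misreading of that kind would do. They do not estimate what will happen.

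**The case against.** The strongest reply is that the entry in 7.2 belongs to a combined template heading in a study without treatment (sections 5 and 6), and most naturally means that there is no treatment to blind. It does not say that scans will be read with the group in view. The cardiology department is a separate institution, the subjects are coded, and no section says that the referral reason, the diagnosis or PISA is sent there. Unaware reading may well be what happens. The flow chart in 7.4 and a figure in 7.3 are not available in the text reviewed, so the flow between the sites cannot be fully checked. Reading rules may also stand in an imaging procedure.

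Most of this stands as a limit on the claim. A reader might infer that cardiology staff will know the group, or that the CCS results will be biased; the protocol supports neither. A reader might also extend the point to EndoPAT staff, and section 7.1.1 largely answers that. How open CCS scoring is to judgement is not described either, so the mechanism of bias is plausible but not documented. The scale figures assume that every error falls in one direction and one group; even then the effect is modest, and this is an unpowered pilot.

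The reply does not remove the core. Separate sites and a code make masking possible but do not establish it, and the one section where it should be stated calls it not applicable. A statistical analysis plan cannot fully repair this later, because masking has to be in place before the scans are read.

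**Conclusion.** The point holds for the CCS reader. Section 7.2 is right on randomisation and treatment allocation and wrong to treat blinding as equally irrelevant. As written, the protocol sets masking aside for an outcome that forms half of the primary correlation, while the exposure is known beforehand.

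The conclusion rests on the wording of 7.2 and on the absence of any masking provision elsewhere in the available text. It does not rest on evidence that readers are informed or that bias has occurred. The size of any bias cannot be derived from the protocol. The change should be made because it protects the primary outcome at very little cost, not because a large distortion has been shown.

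**What to change.** Replace the entry in section 7.2 with text such as:

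> Randomisation and treatment allocation: not applicable. Blinding: CCS is scored and recorded under a subject code that does not indicate group, by existing cardiology staff unaware of reason for referral, periodontal diagnosis and PISA.

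Section 11.1 should then confirm that the two letters of the code carry no information on group.

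The cost is small. The sites are already separate and codes already exist, so no extra reader, visit or analysis is needed, and the sample size is unchanged. The one practical demand is that the group be kept off the imaging request. A corresponding line for EndoPAT is optional.

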7.3 Study procedures

Baseline

Location: PPZ Procedures:

- Patient selection
- Providing information

Periodontal examination

Location: PPZ Procedures:

- Signing informed consent
- **Questionnaire** about medical and dental history, perceived health, parental history, lifestyle, socio-economic status and oral hygiene.
- Periodontal examination: periodontal probing pocket depth (PD), gingival recession, plaque score, and bleeding on probing (BOP) measurements. All measurements will be performed on all teeth, on six sites per tooth. The periodontal inflamed surface area (PISA) will be calculated.
- **Bacterial sample** (on behalf of the microbiome study)

[figure not shown]
Medical examniation

Location: Department of cardiology ISALA Procedures:

- **Physical examination**: Blood Pressure (BP), Heart Rate (HR), Body Mass Index (BMI), Waist to Hip ratio (WHR), Electrocardiogram (ECG)
- Blood sample: HsCRP, total cholesterol, HDL, LDL, triglycerides, eGFR, HbA1c
- **ENDOPAT**: Endothelial function ("EndoScore")
- Extra blood sample for DNA extraction and genotyping (on behalf of the common gene analyses for both diseases)
- Cardiac Computed Tomography (CCT) for Coronary Calcium Scoring (CCS)

Version number: 2,27 March 2013

7.4 Flow chart study procedures

7.5 Withdrawal of individual subjects

Subjects can leave the study at any time for any reason if they wish to do so without any consequences. The investigator can decide to withdraw a subject from the study for urgent medical reasons.

7.6 Replacement of individual subjects after withdrawal

We will not replace individual patients after withdrawal. As this is a cross-sectional pilot study, we will recruit until 50 subjects have been investigated.

7.7 Follow-up of subjects withdrawn from treatment

The reason for withdrawal of each patient will be recorded: further treatment and policy will be performed by the treating dentist and physician.

7.8 Premature termination of the study

Not applicable for this study.

8. SAFETY REPORTING

8.1 Section 10 WMO event

In accordance to section 10, subsection 1, of the WMO, the investigator will inform the subjects and the reviewing accredited METC if anything occurs, on the basis of which it appears that the disadvantages of participation may be significantly greater than was foreseen in the research proposal. The study will be suspended pending further review by the accredited METC, except insofar as suspension would jeopardise the subjects' health. The investigator will take care that all subjects are kept informed.

8.2 Adverse and serious adverse events

If adverse events are encountered, the treating physician is responsible for adequate follow-up. The Practice for Periodontology Zwolle (PPZ) is responsible for the periodontal examination and periodontal treatment.

Adverse events are defined as any undesirable experience occurring to a subject during the study, whether or not considered related to [the investigational product / the experimental treatment]. All adverse events reported spontaneously by the subject or observed by the investigator or his staff will be recorded.

A serious adverse event is any untoward medical occurrence or effect that at any dose:

- results in death;
- is life threatening (at the time of the event);
- requires hospitalisation or prolongation of existing inpatients' hospitalisation;
- results in persistent or significant disability or incapacity:
- is a congenital anomaly or birth defect;
- is a new event of the trial likely to affect the safety of the subjects, such as an unexpected outcome of an adverse reaction, lack of efficacy of an IMP used for the treatment of a life threatening disease, major safety finding from a newly completed animal study, etc.

All SAEs will be reported through the web portal *ToetsingOnline* to the accredited METC that approved the protocol, within 15 days after the sponsor has first knowledge of the serious adverse reactions..

Version number: 2,27 March 2013

SAEs that result in death or are life threatening should be reported expedited. The expedited reporting will occur not later than 7 days after the responsible investigator has first knowledge of the adverse reaction. This is for a preliminary report with another 8 days for completion of the report.

8.2.1 Suspected unexpected serious adverse reactions (SUSAR)

Not applicable for this study.

8.2.2 Annual safety report

Not applicable for this study.

8.3 Follow-up of adverse events

All adverse events will be followed until they have abated, or until a stable situation has been reached. Depending on the event, follow up may require additional tests or medical procedures as indicated, and/or referral to the general physician or a medical specialist.

8.4 Data Safety Monitoring Board (DSMB)

Not applicable for this study.

9. STATISTICAL ANALYSIS

Primary outcome is the correlation between the PISA score and the coronary calcium score. Therefore 2 groups of 25 patients will be analysed. One group diagnosed with periodontal disease and one group with a healthy periodontium. For description of the data the mean values, standard deviations, minimum and maximum are calculated. For continuous data, differences between the groups will be analysed using the independent T-test. If the data violates the assumption of a normal distribution, differences between the groups will be analysed using the Mann-Whitney test. Binary data will be assessed using the Pearson chi-square test. Correlation between the overall PISA score and the coronary calcium score will be calculated with the Spearman correlation test. Outcome variables that show significant between-groups differences at baseline will be used as covariate in a multivariate regression analysis. Data will be entered in a database (SPSS) and analyzed using SPSS statistical package 18.0 (SPSS Inc. Chicago, II

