2. OBJECTIVES

The aim of this study is to determine if there is an association between the PISA score and the coronary calcium score. In other words, whether the presence and the extent of periodontitis is related to the presence and extent of coronary calcification as seen on the coronary calcium score..

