4.4 Sample size calculation

Not applicable. There is no data available on which a sample size calculation can be based. This is a pilot and feasibility study with 50 participants to determine the study population size needed for a full study.

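### One Spearman correlation over 25 periodontitis patients and 25 healthy subjects tests any PISA–CCS association, but cannot tell the extent of periodontitis from its presence

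*Protocol*

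**What the plan says.** Protocol section 2 first asks for an association between PISA and CCS, then restates the aim as "whether the presence and the extent of periodontitis is related to the presence and extent of coronary calcification".

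Section 9 names the primary quantity: "Primary outcome is the correlation between the PISA score and the coronary calcium score". It continues: "Therefore 2 groups of 25 patients will be analysed", and defines the groups: "One group diagnosed with periodontal disease and one group with a healthy periodontium". Groups are compared by t-test or, failing normality, Mann-Whitney. The correlation is then given as "Correlation between the overall PISA score and the coronary calcium score will be calculated with the Spearman correlation test".

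No correlation within the periodontitis group or adjusted for periodontal group is stated. The only adjusted analysis is this: "Outcome variables that show significant between-groups differences at baseline will be used as covariate in a multivariate regression analysis". Periodontal group is not named as a term in it.

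Section 4.4 gives no sample size calculation and describes the 50 participants as a pilot from which a full study will be sized.

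**The concern.** The group comparison speaks to presence. The only stated analysis that could speak to extent is the single Spearman correlation. But the sample is assembled from two groups defined by the disease whose burden PISA measures, so PISA should tend to be low in one and high in the other.

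The null hypothesis of the pooled test is that PISA and CCS are independent over the whole sample. That means no group difference and no gradient. A rejection may come from either, and nothing in section 9 says which.

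A significant correlation could therefore be read as showing that calcification rises with the amount of inflamed tissue, when it only repeats the group comparison. If the pooled coefficient were also used to size a full study of extent, that study would rest on a figure that depends on the 25:25 mix and on how far apart the groups lie on PISA.

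**Working it through.** **Inputs from the protocol.** Two groups of 25, total 50 (section 9); Spearman for PISA and CCS (section 9); presence and extent both in the objective (section 2). There is no stated figure to reproduce.

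**Assumed, because the protocol gives none.** Two-sided 5% level, PISA separation, share of CCS zeros, CCS group difference, and strength of any gradient.

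**1. How much of the PISA ranking is group membership.** With complete separation, the mean ranks are 13 and 38, each 12.5 from the overall mean of 25.5. The variance of ranks 1–50 is (50² − 1)/12 = 208.25. The between-group share is 12.5²/208.25 = 156.25/208.25 = 0.75.

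**2. Rejections with no gradient in either group.** Simulation, 3,000 trials per scenario: latent normal CCS with a group shift, set to zero below the healthy median; PISA independent of CCS within each group.

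| CCS group difference | Pooled, PISA 1.5 SD apart | Pooled, PISA not overlapping |
|---|---|---|
| 0.3 SD | 9% | 13% |
| 0.5 SD | 17% | 28% |
| 0.8 SD | 34% | 60–61% |

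Spearman within the periodontitis group stays at about 5% throughout.

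A second set of runs used PISA separations of 2 and 4 SD and CCS zeros in 0% or 50% of healthy subjects. The pooled test rejected in 22–32% (0.5 SD), 48–63% (0.8 SD) and 66–81% (1.0 SD), with mean coefficients of 0.17–0.39. The within-periodontitis test rejected in 4.5–5.9% and the group-adjusted rank correlation in 4.4–6.4%. Pooled Spearman and Mann-Whitney on CCS gave the same verdict in 81–96% of runs at 4 SD and 67–94% at 2 SD.

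**3. Power when there is a gradient.** The within-patient latent correlation is r.

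| Scenario | r | Pooled | Patients only |
|---|---|---|---|
| Gradient in patients, equal mean CCS | 0.4 | 8–16% | 38–47% |
| | 0.6 | 17–25% | 80–88% |
| Same, plus 0.5 SD group difference | 0.4 | 51–60% | 42–48% |
| | 0.6 | 70–75% | 83–87% |
| Gradient in patients, starting at the healthy level | 0.5 | 92–98% | 65–69% |
| One dose-response over the whole PISA range | 0.4 | 60–62% | 37% |
| | 0.5 | 81% | 54% |
| | 0.6 | 95–96% | 73–74% |

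**4. Precision within the periodontitis group.** Half-width of the 95% CI near zero at n = 25: tanh(1.96/√22) = 0.395, or tanh(1.96 × √(1.06/22)) = 0.406 with the usual Spearman variance inflation. With that variance, 80% power needs a correlation of about 0.55 at n = 25, against 0.40 at n = 50.

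**The case against.** **The test matches the stated aim.** Section 2 asks first for an association between PISA and CCS and offers presence and extent as a paraphrase. PISA is a continuous burden measure whose low end is health, so correlating it over the full range is legitimate. This stands: the pooled Spearman is valid for that question and should not be replaced. The paraphrase still names extent as something to be learned, and the pooled result does not isolate it.

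**A reader might infer that the pooled test misses a real gradient among patients.** The documents do not support this as a general statement. Power is poor only where patients show a gradient yet have about the same mean CCS as healthy subjects, so that the mildest patients would have less calcium than people with a healthy periodontium. Under an ordinary dose-response the pooled test is the more powerful one.

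**A reader might infer that any CCS difference makes the test reject, or that the trial cannot address extent.** Neither follows. The simulated rejection rates are well short of certainty, and PISA and CCS are measured in every participant. Nor may one assume that healthy subjects have no usable PISA spread: groups are not defined by PISA, the protocol gives no PISA distributions, and in a rank test 25 distinct low values spread over the ranks as widely as 25 high ones.

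**Secondary analyses belong in a SAP, and this is a pilot.** Partly stands. A SAP may add them, and section 4.4 concedes "There is no data available on which a sample size calculation can be based", so rejection rates matter less than in a confirmatory trial. But the protocol itself fixes the primary quantity, the two-group sample and the test, and the limit on interpretation follows from those.

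**Wording.** The overall PISA score could mean whole-mouth PISA. One correlation over all 50 remains the natural reading, and no other is described.

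**Conclusion.** The point holds as a limit on interpretation, with an inexpensive improvement available; it is not a fault that invalidates the primary analysis. A significant pooled correlation supports presence and/or extent, not extent as such.

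The 75% share is exact but applies to non-overlapping PISA. The rejection rates without any gradient (9–13%, 17–28% and 34–61% for differences of 0.3, 0.5 and 0.8 SD) depend on the assumed level, zero share and separation, and are lower the more PISA overlaps. Without a CCS group difference the test keeps its level of about 5%. The planned regression cannot be relied on to resolve the matter, because periodontal group is not a stated term.

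**What to change.** In section 9:

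- Keep the pooled Spearman as the overall PISA–CCS association and the group comparison for presence.
- Add a Spearman correlation of PISA and CCS within the periodontitis group, and/or a rank correlation adjusted for periodontal group over all 50, each with a 95% CI.
- State that any claim about extent beyond presence rests on these estimates, and that the pooled coefficient supports only presence and/or extent.

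The two additions are not interchangeable. The adjusted version uses all 50 but averages the gradient over both groups. In the runs with a gradient confined to patients, it detected it in 19–29% (r = 0.4) and 42–54% (r = 0.6), against 38–48% and 80–88% for patients only. Choose one as the main estimate before the data are seen.

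The cost is one or two extra correlations on data already collected and a sentence on interpretation. The downside is precision: about ±0.40 near zero at n = 25, so the pilot's statement about extent becomes more cautious.

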Several epidemiological studies have confirmed the association between periodontitis and atherosclerosis. The first study that found positive epidemiological evidence for this association was in 1989 by Mattila et al.⁴ Bahekar et al. recently summarized the subsequent studies in a systematic review revealing five prospective cohort studies (follow-up >6 years), five case-control studies and five cross-sectional studies. Meta-analysis of the five prospective cohort studies (86092 patients) indicated that individuals with periodontitis had a 1.14 times higher risk of developing coronary heart disease (CHD) than the controls (relative risk 1.14, 95% CI 1.074–1.213, *P* < 0.001). The case–control studies (1423 patients) showed an even greater risk of developing CHD (OR 2.22, 95% CI 1.59-3.117, P < 0.001). The prevalence of CHD in the cross-sectional studies (17724 patients) was significantly greater among individuals with periodontitis than in those without periodontitis (OR 1.59, 95% CI 1.329–1.907, P < 0.001). The individual studies were well be adjusted for confounding factors, because of the extensive documented impact of many prevalent risk factors, shared by periodontitis and CHD. These shared risk factors include increasing age, male sex, race/ethnicity, education and socio-economic status, stress, smoking, alcohol abuse, diabetes mellitus and overweight. 14, 15

Clinical evidence in the literature for the association between periodontitis and atherosclerosis

Observational studies using surrogate endpoints: Periodontitis can correctly be diagnosed and controlled by intra-oral examination (gingival bleeding, pocket-depth, loss of attachment and microbiological sampling or analysis) and dental X-ray (loss of alveolar bone). However, to strictly diagnose atherosclerosis, there is a need of invasive techniques such as angiography of the coronary arteries. Today, several surrogate biomarkers and imaging tools for atherosclerosis are in clinical and experimental use. Since inflammation has emerged as an integrative factor for atherosclerosis, epidemiological studies have found increased vascular risk in association with increased levels of inflammatory biomarkers such as cytokines (IL-6, TNF- α), cell adhesion molecules (P selectin) and acute-phase reactants (CRP, fibrinogen), which are elevated in periodontitis patients.⁷ Growing evidence indicates

Version number: 2 ,27 March 2013 10 of 23

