4.2 Inclusion criteria

- Age 45-70 years
- Male and Female
- All ethnicities
- ≥ 10 teeth

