4.3 Exclusion criteria

- Edentulous
- Known cardiovascular diseases
- Known Diabetes Mellitus
- Known autoimmune disorders
- Known immunosuppressive disorders

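### The primary PISA–calcium correlation is unadjusted although the protocol names age, sex and smoking as shared risk factors, and the planned regression only partly makes up for this.

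*Protocol*

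**What the plan says.** Section 9 defines the target: "Primary outcome is the correlation between the PISA score and the coronary calcium score". It also gives the method: "Correlation between the overall PISA score and the coronary calcium score will be calculated with the Spearman correlation test". The primary method names no covariate, stratum or matching factor.

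The same section plans one adjusted analysis: "Outcome variables that show significant between-groups differences at baseline will be used as covariate in a multivariate regression analysis". It names neither the dependent variable nor whether PISA is in the model.

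Section 1 says the earlier epidemiological studies were adjusted "because of the extensive documented impact of many prevalent risk factors, shared by periodontitis and CHD". It continues: "These shared risk factors include increasing age, male sex, race/ethnicity, education and socio-economic status, stress, smoking, alcohol abuse, diabetes mellitus and overweight".

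Eligibility leaves most of these factors free to vary. Section 4.2 admits "Age 45-70 years" and "Male and Female". Of the listed factors, section 4.3 removes only one: "Known Diabetes Mellitus". Section 7.1.3 collects age, sex and smoking.

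**The concern.** A factor that raises both PISA and coronary calcium produces a positive crude correlation even if the two have no direct link. The protocol names several such factors and cites adjustment for them as a strength of earlier work, yet its own primary statistic does not adjust. The two groups are patients attending one practice for periodontitis or for implants (section 4.1), so balance in age, sex or smoking cannot be presumed.

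Two uses of the result are affected. Section 1 hopes for evidence that periodontitis is a risk indicator for atherosclerosis, and a crude rho cannot separate that from age or smoking. Section 4.4 says the pilot serves to determine the size of a full study, and an inflated rho would make that study too small if the full study targets the adjusted association.

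**Working it through.** **Inputs from the protocol.** N = 50, in two groups of 25. No alpha, power or effect size is stated, so there is no planned figure to reproduce. **Assumed:** two-sided 0.05, and all confounder strengths, shown as ranges.

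**1. Correlation needed for significance.** With 48 df, t = 2.011, so r = t/√(48 + t²) = 2.011/√52.04 = 0.279. On the Fisher scale this is atanh(0.279) = 0.286, with SE = 1/√(50 − 3) = 0.146.

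**2. Crude rho from confounding alone.** Let one shared-risk index correlate a with PISA and b with latent calcium, with PISA and calcium independent given the index. The latent correlation is then a × b, and for normal variables Spearman rho = (6/π)·arcsin(ab/2). For a = 0.3, b = 0.5: ab = 0.15, so rho = 0.14. Simulation (3000 runs per setting, 25 high-PISA and 25 low-PISA subjects, 0% or 40% zero calcium scores) gives:

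| a, b | mean crude rho | crude significant | partial significant |
|---|---|---|---|
| 0.2, 0.3 | 0.06 | 7% | 5–6% |
| 0.3, 0.3 | 0.08–0.09 | 9–10% | 5–6% |
| 0.3, 0.5 | 0.13–0.14 | 16–17% | 5% |
| 0.4, 0.5 | 0.18–0.19 | 25–26% | 5% |
| 0.5, 0.5 | 0.23–0.24 | 36–39% | 5% |
| 0.6, 0.6 | 0.32–0.34 | 64–70% | 5–6% |

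**3. Age, sex and smoking as separate confounders.** Here the periodontitis group is assumed 0.3 to 0.5 SD older, with 40% v 20% smokers and 60% v 40% men, or with weaker imbalances. Across the settings tried, crude rho averaged 0.07 to 0.17 and was significant in 8% to 22% of studies. After partial Spearman it averaged about 0.00, with 5% to 6% significant. The two ends agree with the normal approximation P = Q[(0.286 − z)/0.146] + Q[(0.286 + z)/0.146], where z = atanh(mean rho) and Q is the upper normal tail:

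- rho 0.07: z = 0.070, Q(1.48) + Q(2.44) = 0.069 + 0.007 = 0.076, about 8%.
- rho 0.17: z = 0.172, Q(0.79) + Q(3.14) = 0.216 + 0.001 = 0.217, about 22%.

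The upper end needs all three imbalances in the same direction and sex and smoking each shifting calcification by about 0.6 SD. At 0.4 SD the rate is 16–19%, and at 0.2 SD it is 13%. With all imbalances halved (0.4 SD effects) it is 9%. Age imbalance alone gives 8–11%.

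**4. How well the planned covariate screen works.** Power to flag a difference of d SD with 25 per group is about Φ(d·√12.5 − 1.96). For d = 0.5 this is Φ(1.77 − 1.96) = 42%. It is 18% for d = 0.3 and 81% for d = 0.8. For 20% v 40% smokers it is 33%. If the screen were nevertheless applied to the primary correlation (adjust only for what is flagged), about 5–9% of studies would be significant across the settings tried. In the settings of step 3 the mean rho left over was 0.03 to 0.06.

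**5. Consequence for sizing (illustration).** For 80% power, N = [(1.960 + 0.842)/atanh(rho)]² + 3. Planning on rho 0.30 gives (2.802/0.3095)² + 3 = 85. If the adjusted correlation were 0.15, it would be (2.802/0.1511)² + 3 = 347.

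**6. Price of adjustment.** With three covariates the SE of Fisher z becomes 1/√(50 − 3 − 3) = 1/√44 = 0.151, against 0.146.

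**The case against.** The strongest defence is that section 2 asks only whether PISA and calcium score are associated. If shared risk factors link them, the crude rho is truly non-zero, and detecting it is an error only for someone asking about a direct link. For screening periodontitis patients, a crude association is useful whatever its cause. This stands, and it is why the crude rho should still be reported.

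A reader might infer that the protocol plans no adjustment at all. It does not support that: section 9 contains a regression, and step 4 shows that a screened adjustment would remove much of the bias if it were applied to the primary correlation. What remains is that the regression is not tied to that correlation, leaves its outcome and exposure unnamed, and relies on weak significance tests. Its wording, which speaks of outcome variables, also leaves unclear whether age, sex or smoking qualify.

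A reader might also take one in five as the expected rate of spurious significance. The documents give no imbalances or effect sizes. The 22% is the top of one assumed range, and weak confounding gives 7–10%.

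The study is a pilot with no stated decision rule, and section 4.4 does not say that the crude rho alone will size the full study. So the inflation in step 5 is a possibility, not a stated plan. Finally, a full covariate list may sit in an analysis plan that is not shown. That does not alter the unadjusted primary statistic or the significance-based selection, both of which the protocol itself fixes.

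**Conclusion.** The point holds in a limited form and should be fixed. It does not invalidate the study. The protocol makes an unadjusted correlation its primary result while naming confounders that it records but does not balance, and the planned regression is only a partial repair. The size depends on confounder strengths that the documents do not give. With weak to moderate confounding, no direct link and two-sided 0.05, about 8% to 22% of studies would show a significant crude rho, against about 5–6% after adjustment. Stronger confounding would make it worse, up to 64–70% in the most extreme setting tried. That a positive crude result would be wrong as a statement of association does not follow. What it would lack is separation from age, sex and smoking.

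**What to change.** In section 9, make the primary estimate a partial Spearman correlation of PISA and calcium score adjusted for age, sex and smoking, with a 95% CI. In SPSS this means ranking the variables and then running a partial correlation. Report the crude rho beside it as the descriptive association. Fix the covariates before the data are seen, and drop significance-based covariate selection for this analysis.

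The change needs a sentence or two and no new data. It costs three degrees of freedom, raising the SE of Fisher z from 0.146 to 0.151, about 3% (0.151/0.146 = 1.03). Confounding by factors left out, such as socio-economic status or overweight, remains, so the report should not present the adjusted result as causal.
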